6.2 Preparation and Administration of Selinexor

The Investigator or responsible site personnel must instruct the patient or caregiver to take the study drug as described in this protocol. Study drug will be dispensed to the patient by authorized site personnel only. All dosages prescribed to the patient and all dose changes during the study must be recorded on the Dosage Administration Record eCRF.

Selinexor tablets, with instructions for administration, will be dispensed by study personnel on an outpatient basis.

Patients will be provided with an adequate supply of study drug for self-administration at home until at least their next scheduled study visit.

6.2.1 Drug Name, Formulation and Storage

Recommended INN:	Selinexor
Company's Drug ID:	KPT-330
Chemical name:	(Z)-3-(3-(3,5-bis(trifluoromethyl)phenyl)-1 H -1,2,4-triazol-1-yl)- N' -(pyrazin-2-yl)acrylohydrazide
Classification:	Cell biological modifier: Apoptosis-inducing agent
Mechanism of action:	Selinexor is a Selective Inhibitor of Nuclear Export/SINE compound that specifically blocks nuclear export by reversible covalent binding to XPO1 protein.
Molecular formula:	C ₁₇ H ₁₁ F ₆ N ₇ O
Molecular weight:	443.31
Approx. solubility:	< 0.03 mg/mL in water (pH 2-8) > 10 mg/mL in dimethylsulfoxide < 2 mg/mL in 40% v/v PEG-400/ H ₂ O < 2 mg/mL in 15% v/v EtOH/ H ₂ O

Tablets:

Selinexor (KPT-330) for oral administration will be supplied in up to three (3) tablet strengths: 10 mg, 20 mg, and 25 mg. Bulk bottles of 50 tablets per bottle will be supplied to the pharmacies for both the 10 mg and 25 mg strength tablets. The 20 mg tablets will be provided in blister packs when available.

Labeling:

Each bottle or blister pack of selinexor tablets will be labeled in accordance with current ICH guidelines and specific national requirements.

Storage:10 mg and 25 mg Tablets

Selinexor tablets will be supplied in white high-density polyethylene (HDPE) bottles with induction seals and desiccant. They will be stored at ambient temperatures between 5–30 °C in a locked and secured area with restricted access to study staff. Do not freeze.

20 mg Tablets

Selinexor tablet blister packs can be stored at room temperature or refrigerated, at or below 86 °F or 30 °C, but not frozen. Room temperature storage is recommended. The study site will be required to maintain documentation of the temperature and/or temperature excursions where the study medication is stored.

6.2.2 Administration of Study Drug

The dose of selinexor to be administered will be determined, by patient, on a mg/m² basis, based on the patient's actual calculated body surface area (BSA) at baseline. Patients with a BSA > 2.5 m² will receive a dose based upon a 2.5 m² BSA.

Primary Treatment Phase*Dose Schedules in Parts 1 and 2:*

- Part 1: Selinexor tablets will be dosed at 50 mg/m² orally twice weekly (e.g., Monday and Wednesday, Tuesday and Thursday, Wednesday and Friday or Thursday and Saturday) in each week of a 4-week cycle.
- Part 2:
 - *Schedule 1* – Selinexor tablets will be dosed orally at 35 mg/m² twice weekly (e.g., Monday and Wednesday, Tuesday and Thursday, Wednesday and Friday or Thursday and Saturday) in each week of a 4-week cycle.
 - *Schedule 2* - selinexor will be dosed orally at 50 mg/m² once weekly (e.g., Monday of each week) in each week of a 4-week cycle.

Once- and Twice-weekly Dose Schedules:

- Twice-weekly dose schedules (Part 1 and Part 2 Schedule 1): Eight (8) doses of selinexor will be administered, ≥ 36 hours apart, during each 28-day (4-week) cycle.
- Once-weekly dose schedules (Part 2 Schedule 2): Four (4) doses of selinexor will be administered, ≥ 5 days apart, in each 28-day (4-week) cycle.

Selinexor should be taken with a light meal (to optimize tolerability) together with 120 mL (4 ounces) of water.

Maintenance Phase: See Section 18 (Appendix 16) for study treatment during the Maintenance Phase of the study (Version ≥ 3.2).

6.2.3 Compliance

The Investigator should ensure that the investigational product is used only in accordance with the protocol. All doses given are to be documented in the eCRF, including exact dose, number of tablets, time and date administered. The principal Investigator or the designee will account for the number of tablets dispensed against those stored at the site. Any deviations and missed doses will be recorded in the eCRF and drug accountability logs for verification with the reasons for missed doses. The Investigator/ designee will try to ensure complete compliance with the dosing schedule by providing timely instructions to the patients. It will be requested from patients to document intake of selinexor in a patient diary.

The investigational product should be stored as specified by the sponsor and in accordance with applicable regulatory requirements.

6.3 Dose Modifications for Selinexor

See Section 18 (Appendix 16) for supportive care and dose modification recommendations during the Maintenance Phase of the study (Version ≥3.2).

Toxicity will be graded according to NCI CTCAE, v.4.03; the therapy modifications described below are applied according to this severity grading.

If more than one different type of toxicity occurs concurrently, the most severe grade will determine the modification.

Re-escalation of the study drug is only allowed as outlined in the sections that apply for the specific toxicity. If toxicity requires a treatment delay of more than 4 weeks the patient is taken off protocol treatment.

Each dose modification or treatment delay has to be documented in the eCR, including the respective reason.

Based on observations from the ongoing Phase 1 studies in patients with advanced hematological and solid tumors, selinexor (KPT-330) shows a wide therapeutic range, with documented anti-cancer activity from ~ 12 mg/m² to ≥ 50 mg/m² orally twice weekly. At the time of Part 1 it could not be predicted which patient's tumors would respond to lower doses, nor could tolerability be predicted. Therefore, in order to individualize and optimize therapeutic benefit with selinexor, initiation of study therapy occurred at a dose just below the MTD (50 mg/m² twice weekly by mouth). To optimize specific anti-tumor activity and the patient's tolerability, dose and/or schedule modifications were allowed. Based on preliminary findings from this study and other studies, the dosing in Part 2 was modified as follows: Part 2 Schedule 1 to 35 mg/m² twice weekly, Part 2 Schedule 1 to 50 mg/m² once weekly. Dose modifications are allowed as described in Table 2 and Table 3.

Patients should also be treated aggressively with supportive care to reduce toxicities.

Patients will continue to receive selinexor until they need to have their dose reduced below the 35 mg/m² once weekly (reduced) dose in Part 1 and Part 2 (Schedules 1 and 2), at which time treatment will be discontinued.

Table 2: Pre-specified Dose/Schedule Modifications for AEs Related to Study Drug in Part 1

Dose Level	Dose of Selinexor
Dose level 0	50 mg/m ² twice weekly (D1, D3)
Dose level -1	35 mg/m ² twice weekly (D1, D3)
Dose level -2	50 mg/m ² once weekly (D1)
Dose level -3	35 mg/m ² once weekly (D1)
Dose level -4	Discontinue dosing ^a

^a Patient discontinues treatment, but continues to be assessed.

Table 3: Pre-specified Dose/Schedule Modifications for AEs Related to Study Drug in Part 2

Dose Level	Schedule 1	Schedule 2
Dose level 0 (Starting dose)	35 mg/m ² twice weekly	50 mg/m ² once weekly
Dose level -1	50 mg/m ² once weekly	35 mg/m ² once weekly
Dose level -2	35 mg/m ² once weekly	Discontinue dosing ^a
Dose level -3	Discontinue dosing ^a	Not applicable

^a Patient discontinues treatment, but continues to be assessed.

6.3.1 Inpatient Dose Escalation:

Inpatient dose escalation can be considered after 12 weeks for patients in Part 1 and after 6 weeks for patients in Part 2 if the patient has not experienced a major toxicity; this requires approval of the Sponsor. Inpatient dose escalations will be permitted as follows:

Part 1: Dose increase to 60 mg/m² twice weekly in each week of a 4-week cycle.

Part 2 Schedule 1: Dose increase to 50 mg/m² twice weekly in each week of a 4-week cycle (8 doses total).

Part 2 Schedule 2: Dose increase to 60 mg/m² once weekly in each week of a 4-week cycle (4 doses total).

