Grade ≥ 3 (Grade 4 for emesis only)	As in grade 2; if symptoms persist hold dose until nausea and vomiting resolve to grade 1 or baseline. Restart dose of selinexor, one dose below. Start NK1R antagonist as prophylaxis next cycle.	As in grade 2; if symptoms persist hold dose until nausea and vomiting resolve to grade 1 or baseline. Restart dose of selinexor, one dose below. Start NK1R antagonist as prophylaxis next cycle.	As in grade 2; if symptoms persist hold dose until nausea and vomiting resolved to grade 1 or baseline. Restart dose of selinexor, one dose below. Start NK1R antagonist as prophylaxis next cycle.
Hematologic			
Neutropenia			
Grade ≤ 3	
 Maintain dose level The use of growth factors during selinexor treatment is permitted and in patients with poor marrow function, encouraged. If ANC drops to < 1000/mm³, growth factors are encouraged to reduce dose interruptions. 	
 Maintain dose level The use of growth factors during selinexor treatment is permitted and in patients with poor marrow function, encouraged. If ANC drops to < 1000/mm³, growth factors are encouraged to reduce dose interruptions. 	
 Maintain dose level The use of growth factors during selinexor treatment is permitted and in patients with poor marrow function, encouraged. If ANC drops to < 1000/mm³, growth factors are encouraged to reduce dose interruptions.

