
Grade 1 (Lower Limit of Normal to 130 nM)
	
Maintain dose level, assure adequate fluid, electrolyte and caloric intake, adjust other medications, consider salt supplementation, rule out other causes.
	
Maintain dose level, assure adequate fluid, electrolyte and caloric intake, adjust other medications, consider salt supplementation, rule out other causes.
	
Maintain dose level, assure adequate fluid, electrolyte and caloric intake, adjust other medications, consider salt supplementation, rule out other causes.

Grade ≥ 3 (120-130 nM)
	
Discontinue selinexor until resolved to grade ≤ 1, then reduce dose by 1 level. Check renal function, serum, and urinary electrolytes, and rule out other causes.
	
Discontinue selinexor until resolved to grade ≤ 1, then reduce dose by 1 level. Check renal function, serum, and urinary electrolytes, and rule out other causes.
	
Discontinue selinexor until resolved to grade ≤ 1, then reduce dose by 1 level. Check renal function, serum, and urinary electrolytes, and rule out other causes.

AST or ALT (rare)
			

Grade 1 (> ULN - 2.5 x ULN)
	
Maintain dose level
	
Maintain dose level
	
Maintain dose level

Grade 2 (> 2.5 - 5.0 x ULN)	Delay selinexor until resolved to grade \leq 1 or baseline, then maintain dose level. Consider addition of S-adenosylmethionine (SAM) 400 mg qd-bid.	Delay selinexor until resolved to grade \leq 1 or baseline, then maintain dose level. Consider addition of S-adenosylmethionine (SAM) 400 mg qd-bid.	Delay selinexor until resolved to grade \leq 1 or baseline, then maintain dose level. Consider addition of S-adenosylmethionine (SAM) 400 mg qd-bid.

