Grade 3 (> 5.0 - 20.0 x ULN)	
 1. Delay selinexor until resolved to \leq grade 2 or baseline, then reduce by 1 dose level (Table 2 & Table 3) 2. Consider addition of S-adenosylmethionine (SAM) 400 mg qd-qid. 3. If no further AST or ALT elevations occur during one cycle (4 weeks) at the reduced dose level, then dose may be continued at the reduced dose. 4. Discontinuation of selinexor is required if concurrent elevations of direct bilirubin > 2.0 X upper limit of normal (ULN) and ALT or AST > 3.0 X ULN are observed. 5. In order to characterize hepatic toxicity more precisely, fractionation of bilirubin and alkaline phosphatases will be required for elevated values > 2.0 X ULN and \geq CTCAE grade 2, respectively. 	
 1. Delay selinexor until resolved to \leq grade 2 or baseline, then reduce by 1 dose level (Table 2 & Table 3) 2. Consider addition of S-adenosylmethionine (SAM) 400 mg qd-qid. 3. If no further AST or ALT elevations occur during one cycle (4 weeks) at the reduced dose level, then dose may be continued at the reduced dose. 4. Discontinuation of selinexor is required if concurrent elevations of direct bilirubin > 2.0 X upper limit of normal (ULN) and ALT or AST > 3.0 X ULN are observed. 5. In order to characterize hepatic toxicity more precisely, fractionation of bilirubin and alkaline phosphatases will be required for elevated values > 2.0 X ULN and \geq CTCAE grade 2, respectively. 	
 1. Delay selinexor until resolved to \leq grade 2 or baseline, then reduce by 1 dose level (Table 2 & Table 3) 2. Consider addition of S-adenosylmethionine (SAM) 400 mg qd-qid. 3. If no further AST or ALT elevations occur during one cycle (4 weeks) at the reduced dose level, then dose may be continued at the reduced dose. 4. Discontinuation of selinexor is required if concurrent elevations of direct bilirubin > 2.0 X upper limit of normal (ULN) and ALT or AST > 3.0 X ULN are observed. In order to characterize hepatic toxicity more precisely, fractionation of bilirubin and alkaline phosphatases will be required for elevated values > 2.0 X ULN and \geq CTCAE grade 2, respectively.
Grade 4 (> 20.0 x ULN)	Delay selinexor until resolved to \leq grade 2, then reduce by 2 dose levels.	Delay selinexor until resolved to \leq grade 2, then reduce by 2 dose levels.	N/A
Diarrhea (common)			

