Grade 1 (despite maximal anti-diarrheal medication)	At the first sign of abdominal cramping, loose stools, or onset of diarrhea, it is recommended that the patient be treated according to institutional standard of care. Maintain dose level of selinexor.	At the first sign of abdominal cramping, loose stools, or onset of diarrhea, it is recommended that the patient be treated according to institutional standard of care. Maintain dose level of selinexor.	At the first sign of abdominal cramping, loose stools, or onset of diarrhea, it is recommended that the patient be treated according to institutional standard of care. Maintain dose level of selinexor.

Grade 2 (despite maximal anti-diarrheal medication)	First occurrence: reduce selinexor to once weekly until resolved to ≤ grade 1, then re-start twice weekly at the current dose level. Second occurrence: reduce selinexor dose by one dose level and dose once weekly until resolved to ≤ grade 1, then re-start twice weekly at reduced dose level	First occurrence: reduce to selinexor to once weekly until resolved to ≤ grade 1, then re-start twice weekly at the current dose level. Second occurrence: reduce selinexor dose by one dose level and dose once weekly until resolved to ≤ grade 1, then re-start twice weekly at reduced dose level	First occurrence: reduce selinexor to 35 mg/m ² until resolved to ≤ grade 1 or baseline, then re-start at the Dose level 0. Second occurrence: reduce one dose level
Grade 3/4 (despite maximal anti-diarrheal medication)	Delay selinexor until resolved to ≤ grade 2 or baseline, then follow guidelines above.	Delay selinexor until resolved to ≤ grade 2 or baseline, then follow guidelines above.	Delay selinexor until resolved to ≤ grade 2 or baseline then reduce one dose level.
Other selinexor-related adverse events			
Grade 1 or 2	Maintain dose level and initiate standard supportive care.	Maintain dose level and initiate standard supportive care.	Maintain dose level and initiate standard supportive care.
Grade 3	Delay dose until resolved to ≤ grade 1 or baseline, then reduce by one dose level.	Delay dose until resolved to ≤ grade 1 or baseline, then reduce by one dose level.	Delay dose until resolved to ≤ grade 1 or baseline, then reduce to Dose level -1.

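### Section 6.3 lets the highest grade choose the dose action for concurrent toxicities, but in Table 4 a higher grade sometimes carries the milder action

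*Protocol*

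**What the plan says.** Protocol section 6.3 grades toxicity by CTCAE v4.03 and ties modifications to that grading. For combinations it states: "If more than one different type of toxicity occurs concurrently, the most severe grade will determine the modification". The same section names modification and delay as separate things: "Each dose modification or treatment delay has to be documented in the eCR".

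Table 4 in section 6.3.2 gives the action for each toxicity and grade, in three columns (Part 1, Part 2 Schedule 1, Part 2 Schedule 2). The rows that matter are:

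- Neutropenia, Grade 3 or lower: "Maintain dose level The use of growth factors during selinexor treatment is permitted". No column asks for a hold or reduction. Febrile neutropenia has its own row, with a delay and a one-level reduction.
- Neutropenia, Grade 4: delay until the count exceeds 800/mm³, then resume at the same level if that takes 7 days or less, and one level lower if it takes longer.
- Diarrhea, Grade 2 despite maximal medication, in Part 1: "First occurrence: reduce selinexor to once weekly until resolved to" Grade 1 or lower, then back to twice weekly. Schedule 1 has the same action. Schedule 2 drops to 35 mg/m² and later returns to Dose level 0.
- Hyponatremia, Grade 3 or higher: stop until Grade 1 or lower, then resume one level lower.
- AST/ALT, Grade 2: "Delay selinexor until resolved to grade" 1 or lower, or baseline, after which the dose level is maintained.
- Fatigue Grade 3 and anorexia Grade 3 or higher: interrupt only if symptoms have not resolved within 7 days.

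A note under Table 4 bases modifications on the worst toxicity that came before, without defining worst. No section says that the most restrictive action governs. The SAP adds no rule of its own; its section 1.2.1.1 refers back to protocol section 6.3.

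**The concern.** Choosing the action by grade is safe only if actions become stricter as grade rises across different toxicities, and not just within one row. If that fails, a patient who develops a second, higher-grade toxicity can be dosed less cautiously than the first toxicity alone would require.

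The literal rule carries weight. Section 6.2.3 asks investigators to use the product only as the protocol lays down, and section 6.3 describes the Part 1 starting dose as just below the maximum tolerated dose. What is at stake is patient safety and consistent dosing between sites. No statistical estimate is at stake.

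**Working it through.** The protocol gives no figure to reproduce, so the check sets rows of Table 4 side by side. For each pair, find the higher grade, read the action in that row, and compare it with the action the other toxicity would require on its own.

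| Combination | Row chosen by 6.3 | Action that follows | Action the other row requires alone | Result |
|---|---|---|---|---|
| Grade 3 neutropenia without fever + first Grade 2 diarrhea | Neutropenia (3 > 2) | Same dose level | Once weekly (Part 1, Schedule 1) or 35 mg/m² (Schedule 2) until Grade 1 or lower (Schedule 2: or baseline) | Reduction lost in all three columns |
| Grade 4 neutropenia recovering within 7 days + Grade 3 hyponatremia | Neutropenia (4 > 3) | Delay, then same dose level | Stop until Grade 1 or lower, then one level lower | One-level reduction lost in all three columns |
| Grade 3 neutropenia without fever + Grade 2 AST/ALT | Neutropenia (3 > 2) | Same dose level | Hold, then same dose level | Hold lost only if keeping the level excludes a hold |
| Grade 3 fatigue or anorexia + Grade 2 AST/ALT | Fatigue or anorexia (3 > 2) | Interrupt only if unresolved within 7 days | Hold now | Hold postponed only on the same kind of reading |

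**First pair.** The two actions cannot both be followed. At the starting dose, the Schedule 2 diarrhea action (35 mg/m² once weekly) is dose level -1 in Table 3. In Part 1, 50 mg/m² once weekly is dose level -2 in Table 2. In Schedule 1, 35 mg/m² once weekly is dose level -2 in Table 3. The Part 1 and Schedule 1 rows speak of restarting at the current dose level, so one could call their step a change of frequency. The Schedule 2 step is plainly a change of dose level.

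**Second pair.** The Grade 4 neutropenia row fixes the restart level as unchanged. The hyponatremia row fixes it one level lower. Both cannot hold.

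**Third and fourth pairs.** These differ. The Grade 2 AST/ALT row itself joins a delay to keeping the dose level, as does Grade 4 neutropenia with quick recovery. In this table the phrase can therefore set the level at which dosing continues or resumes, without forbidding a pause. A patient held for AST/ALT and restarted at the same level has satisfied both rows.

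**The Table 4 note.** If worst means highest grade, the note repeats the rule. If it means something else, it is undefined. Neither meaning makes the stricter action govern.

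**Equal grades.** The rule is silent there. That is a gap and not an inversion, and it is not counted.

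**The case against.** The strongest reply is that a modification in section 6.3 means an actual change of dose. Section 6.3 points to Tables 2 and 3 for permitted modifications, and below the starting dose those list only reductions and discontinuation. Keeping the dose would then be no modification and could not displace one. The Table 4 column heading does not refute this, because the same column also contains diet advice, IV fluids and antiemetics. Nothing forbids an investigator from acting on the stricter row. Further protection comes from sponsor consultation (3.1.1), removal from treatment at investigator discretion (5.5), repeat testing of unexplained abnormal values (7.1.3) and the Safety Monitoring Committee (14).

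This reading is possible, and many investigators would probably act on it, which lowers the likely harm. It does not repair the sentence. The rule says that the highest grade decides, and the neutropenia row at that grade does give an instruction about dose level. The narrow reading would also let the hyponatremia reduction through, but only by ignoring the restart level that the Grade 4 neutropenia row prescribes.

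The objection succeeds on a stronger claim that a reader might infer: that the rule cancels the Grade 2 AST/ALT hold outright. The documents do not support that, because the AST/ALT row is compatible with keeping the dose level and section 6.3 names delays separately. The 7-day waits for fatigue and anorexia fall with it, since nothing says that a hold for another toxicity must wait for them. The hepatic stakes are also limited. Table 4 labels AST/ALT elevation rare, section 6.5.3 says significant liver toxicity had not been reported, and the Grade 3 AST/ALT row requires discontinuation when defined bilirubin and transaminase elevations coincide. That last safeguard does not cover an isolated Grade 2 elevation.

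It is also fair to note that Table 4 gives neutropenia, the trigger in both clear inversions, no frequency label, and that section 6.5.2 does not list it among the main side effects.

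**Conclusion.** Wrong as written, minor. Two inversions stand: non-febrile Grade 3 neutropenia over a first Grade 2 diarrhea, and quickly recovering Grade 4 neutropenia over Grade 3 hyponatremia. The AST/ALT and 7-day cases are conditional on one reading. The conclusion assumes that severity means CTCAE grade, as section 6.3 indicates, and that keeping a dose level is incompatible with reducing it.

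The reach is small. The diarrhea reduction is temporary. Section 1.4 reports 3 patients on treatment in July 2016, and under Appendix 16 they complete the current cycle and move to the Maintenance Phase, where dose changes are discussed with the Medical Monitor.

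Two further inferences are not supported. One is an amount of excess drug: the documents say neither how often these combinations occur nor how long they last, so multiplying weekly doses by an assumed duration would only restate the schedules. The other is bias in the Part 2 comparison: the inversions appear in both schedules, and nothing shows that they fall unequally.

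**What to change.** Replace the sentence in section 6.3, and align the Table 4 note, with wording such as:

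*When several toxicities are present together, apply the most restrictive Table 4 action among them (discontinue, then hold, then reduce, then maintain), whatever their grades. Resume only when each toxicity meets its own restart criterion, at the lowest dose level that any of them requires.*

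Add that the hyponatremia instruction to discontinue until resolution counts as a hold. Otherwise the ordering would turn it into permanent discontinuation.

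The cost is one sentence and one note, with no extra patients or procedures. The change has to go through the amendment process in section 11. The clinical downside is an occasional longer hold or additional reduction. A longer hold could reach the existing limit (4 weeks in section 6.3, 28 days in the Table 4 notes), after which the patient comes off treatment.
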